1 INTRODUCTION

This Statistical Analysis Plan (SAP) provides details on planned study statistical analyses and reports for HPTN 077. This SAP is required prior to the first analysis and must be approved by the protocol chair and reviewed by GSK statistician. The plan might be updated if needed prior to any interim analyses and before the final analysis. Any updates will be archived. The contents of SAP are based on the protocol HPTN 077 final version 3.0 and are modified to extend the tail visits according to Letter of Amendment #3.

2 PROTOCOL SUMMARY

2.1 Title

A Phase IIa Study to Evaluate the Safety, Tolerability and Pharmacokinetics of the Investigational Injectable HIV Integrase Inhibitor, GSK1265744, in HIV-uninfected Men and Women

2.2 Primary Objectives

- Evaluate the safety and tolerability of the injectable agent GSK1265744 long acting (744LA) injectable (800 mg dose administered at three time points at 12 week intervals), through Week 41 in HIV-uninfected men and women.
- Evaluate the safety and tolerability of the injectable agent GSK1265744 long acting (744LA) injectable (600 mg dose administered at two time points at 4 week intervals, followed by three time points at 8 week intervals), through Week 41 in HIV-uninfected men and women.

2.3 Study Product Regimens/Administration/Formulation Content

Study Product Regimens

Both Cohorts:

Oral lead-in phase: Participants will be randomized 3:1 to one of two study arms:

- Arm 1: GSK1265744 tablets 30 mg – one tablet orally daily for 4 weeks, with or without food
- Arm 2: Placebo for GSK1265744 – one tablet orally daily for 4 weeks, with or without food

Injectable phase: After a one week washout period to assess safety, participants will begin injections (with the same randomization as the oral lead-in phase) as:

Cohort 1:

- Arm 1: GSK1265744 (744 LA) 800 mg administered as two 2 mL (400 mg) IM injections in the gluteal muscle at Weeks 5, 17, and 29

- Arm 2: Placebo for GSK1265744 (744 LA Placebo) administered as two 2 mL injections in the gluteal muscle at Weeks 5, 17, and 29

Cohort 2:

- Arm 1: GSK1265744 (744 LA) 600 mg administered as one 3mL (600 mg) IM injections in the gluteal muscle at Weeks 5, 9, 17, 25 and 33
- Arm 2: Placebo for GSK1265744 (744 LA Placebo) administered as one 3 mL injections in the gluteal muscle at Weeks 5, 9, 17, 25 and 33

Study Product Formulations

Oral product:

- GSK1265744 tablets 30 mg are formulated as white to almost white oval-shaped coated tablets for oral administration. The tablets are packaged in high density polyethylene (HDPE) bottles with child-resistant closure that include an induction seal. The bottles contain a desiccant. The bottles should be stored up to 25 degrees Celsius (25° C) and protected from moisture.
- Placebo tablets for GSK1265744 are formulated as white to almost white oval-shaped coated tablets to visually match the active GSK1265744 tablets. The tablets are packaged in high density polyethylene (HDPE) bottles with child-resistant closure that include an induction seal. The bottles contain a desiccant. The bottles should be stored up to 25 degrees Celsius (25° C) and protected from moisture.

Injectable Suspension:

[figure not shown]
- The GSK1265744LA is formulated as a sterile white to slightly colored suspension containing 400mg/2mL of GSK1265744 for administration by intramuscular (IM). The product is packaged in a 3 mL vials. Each vial is for single use containing a nominal fill of 2mL (400 mg), and does not require dilution prior to administration. The GSK1265744LA injectable suspension is to be stored at 2 degrees Celsius to 30 degrees Celsius (2° C – 30° C), do not freeze.
- Placebo for GSK1265744 Injectable Suspension will be Sodium Chloride for Injection USP, 0.9%.

Syringes containing active and placebo study product will be covered with an overlay by the study Pharmacist of Record or designee prior to dispensing in order to maintain the blind, as per the SSP Manual.

The study product being tested in this study is investigational and not yet approved by the US FDA for the treatment or prevention of HIV-1 infection. Further information on the study product is available in the Investigator's Brochure, which will be provided by the DAIDS Regulatory Support Contract (RSC).

[figure not shown]
2.4 Schema

Cohort 1

W = Week

Cohort 2

The 110 participants in Cohort 1 and 90 participants in Cohort 2 were randomized to one of the two study arms with an active GSK 744 to placebo ratio of 3:1, stratified by gender and region (US and non US), as follows:

Cohort 1

Arm 1: 82 participants received daily oral 744 (30 mg tablets) for 4 weeks, followed by an one week washout period, to establish safety and tolerability, followed by intra-muscular (IM) gluteal injections of 800 mg of 744LA (administered as two sequential 400 mg gluteal injections) at three time points at 12 week intervals as: Week 5, Week 17, and Week 29.

Arm 2: 28 participants received daily oral matching placebo and IM injections of vehicle-matched placebo on the same schedule as Arm 1.

Cohort 2

Arm 1: Approximately 66 participants will receive daily oral 744 (30 mg tablets) for 4 weeks, followed by a one week washout period, to establish safety and tolerability, followed by intra-muscular (IM) gluteal injections of 600 mg of 744LA (administered as one 600 mg gluteal injection) at five time points at 4 and 8 week intervals as: Week 5, Week 9, Week 17, Week 25, and Week 33.

Arm 2: Approximately 22 participants will receive daily oral matching placebo and IM injections of vehicle-matched placebo on the same schedule as Arm 1.

All participants will receive HIV testing with pre- and post-test counseling, in addition to risk-reduction counseling and condoms and lubricant. All participants will be followed according to the Schedule of Evaluations and Procedures provided in HPTN077 protocol Appendices I-IV.

3 OBJECTIVES AND ENDPOINTS

3.1 Primary Objectives and Endpoints

Primary Objective

- Evaluate the safety and tolerability of the injectable agent, GSK1265744 long acting (744LA) injectable (800 mg dose administered at three time points at 12 week intervals) through Week 41 in HIV-uninfected men and women
- Evaluate the safety and tolerability of the injectable agent GSK1265744 long acting (744LA) injectable (600 mg dose administered at two time points at 4 week intervals, followed by three time points at 8 week intervals), through Week 41 in HIV-uninfected men and women.

Primary Endpoints

Safety endpoint: Proportion of participants experiencing any Grade 2 or higher clinical AEs and laboratory abnormalities that occur from the initial injection to 12 weeks after the last injection among participants who receive at least one injection (injectable phase only)

Tolerability endpoint: Proportion of participants who receive at least 1 injection and who discontinue receiving injections prior to the full course of 3 injections due to intolerance of injection (including but not limited to ISR), frequency of injections, burden of study procedures, or any AE.

These cohorts may be aggregated for an overall analysis if appropriate.

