7 ASSESSMENT WINDOWS

7.1 Treatment Periods

Adverse events, laboratory, vital signs and liver events will be assessed and denoted within the treatment periods that are defined below.

Oral Phase is defined as the time between the enrollment date (Week 0) and the day of the 1st injection (Week 5) or the day of withdrawal, whichever comes first.

Injection Phase is defined as the time between the first injection and the 12 weeks visit after the last injection. For the participants who complete all three injections, the injection phase assessment window is the time between Week 5 and Week 41 visits. For the participants who complete the two injections, the injection phase assessment window is the time between Week 5 visit and Week 29 visit. For the participants who complete only the first injection, the injection phase assessment window is the time between Week 5 visit and Week 17 visit.

Tail Phase is defined as the time between Week 41 to Week 105/109 for ITT analysis. However, for per protocol analysis such as pharmacokinetics analysis, for the participants who did not complete full injections (3 injections for cohort 1 and 5 injections for cohort 2), the tail phase assessment window starts at the 12th (the 8th) weeks after the last injection for cohort 1 (cohort 2) to the last follow-up visit.

On-Treatment is defined as the time between the beginning of the oral phase and the end of the follow-up phase (from the participants' enrollment day to the participants' last day subject's last day in the study).

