9.5.5 Safety Endpoint

Primary safety endpoint is the proportion of participants experiencing any Grade 2 or higher clinical AEs or laboratory abnormalities since the initial injection to 12 weeks (8 weeks) after the last injection in Cohort 1 (Cohort 2) among the participants who complete at least one injection to evaluate the safety of the 744 injectable during the injection phase. A secondary safety endpoint is the proportion of Grade 2 or higher clinical AEs or laboratory abnormalities occurred from the initial injection to 76 weeks in both cohorts after last injection among the participants who complete at least one injection to evaluate the safety of the 744 injectable in long term; the proportion of Grade 2 or higher AEs or laboratory abnormalities occurred during the oral phase (Weeks 0-5) among all enrolled participants to evaluate the safety of the oral 744 product; and the proportion of Grade 2 or higher AEs or laboratory abnormalities occurred during the whole study period among the all enrolled participants to evaluate the safety of the oral and injectable product. The proportions of endpoints and the %95 confidence intervals will be estimated for each treatment arm. The 95% CIs will be estimated using Wilson score method¹. The proportions of endpoints will be compared between the treatment arms using Fisher Exact test.

In addition, the safety endpoint rate might be calculated for each treatment arm and compared between the treatment arms. The safety endpoint rate is the number of the participants who have experienced Grade 2 or higher clinical AEs or laboratory abnormalities during the study period (defined in each safety analysis) divided by the person-time-at-risk throughout the observation period within the study period.

The 95% exact confidence interval of the safety event rate will be calculated for each treatment arm, assuming the rate follows the Poisson distribution. The safety event rate will be compared between the treatment arms using exact Poisson test.

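### For Cohort 2 the primary safety endpoint has two end rules: 12 weeks after the last injection in SAP 3.1 and 7.1, 8 weeks in 9.5.5

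*SAP*

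**What the plan says.** Three sections of the SAP fix the end of the primary safety window.

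- Section 3.1 counts, besides clinical AEs, "laboratory abnormalities that occur from the initial injection to 12 weeks after the last injection among participants who receive at least one injection". The objectives just above it name both regimens, but the window is not split by cohort.
- Section 7.1 agrees: "Injection Phase is defined as the time between the first injection and the 12 weeks visit after the last injection". It then prints end weeks by number of injections, starting with the longest: "For the participants who complete all three injections, the injection phase assessment window is the time between Week 5 and Week 41 visits". The other two are Week 29 after two injections and Week 17 after one. Nothing is printed for four or five injections.
- Section 9.5.5, which specifies the analysis, runs the same endpoint "since the initial injection to 12 weeks (8 weeks) after the last injection in Cohort 1 (Cohort 2"). Its optional event rate is a count "divided by the person-time-at-risk throughout the observation period within the study period".

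Section 7.1 also fixes where the next phase starts: "Tail Phase is defined as the time between Week 41 to Week 105/109 for ITT analysis". For per-protocol analyses of participants with an incomplete course, "the tail phase assessment window starts at the 12th (the 8th) weeks after the last injection for cohort 1 (cohort 2").

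**The concern.** The 12-week and 8-week rules cannot both be programmed for Cohort 2. A participant whose first Grade 2 or higher event falls between Weeks 41 and 45 after a full course is an endpoint case under 3.1 and 7.1 but not under 9.5.5. The person-time for the 9.5.5 event rate changes with the same choice. A programmer who turns to 7.1 for end weeks finds a set written for the three-injection course and nothing that places a participant with four or five injections. The endpoint is primary and one of the two cohorts is affected, so the choice should not be left to whoever writes the code.

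**Working it through.** **Inputs.** Injection weeks (SAP 2.3 and 2.4): Cohort 1 at 5, 17, 29; Cohort 2 at 5, 9, 17, 25, 33. Visits (4.4): Cohort 2 has Week 41 and then Week 53. End week = week of last injection + 12 or + 8. Window length = end week − 5.

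**The SAP's own figures.** Cohort 1 with 12 weeks: 5 + 12 = 17, 17 + 12 = 29, 29 + 12 = 41. All three end weeks printed in 7.1 are reproduced.

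**Cohort 2 under each rule.**

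| Injections received | Last injection (week) | End, +8 (9.5.5) | End, +12 (3.1, 7.1) | Length, +8 | Length, +12 | Extra |
|---|---|---|---|---|---|---|
| 1 | 5 | 13 | 17 | 8 | 12 | 4/8 = 50% |
| 2 | 9 | 17 | 21 | 12 | 16 | 4/12 = 33% |
| 3 | 17 | 25 | 29 | 20 | 24 | 4/20 = 20% |
| 4 | 25 | 33 | 37 | 28 | 32 | 4/28 = 14% |
| 5 | 33 | 41 | 45 | 36 | 40 | 4/36 = 11% |

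Neither column gives the printed set 17, 29, 41 for one, two and three injections. Week 17 after one injection does match the 12-week rule (5 + 12), so the misfit concerns the set and not every value in it.

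**Full course against the rest of the SAP.** Week 41 is the end of the primary objective (3.1), the primary endpoint visit in both cohorts (4.4), the time point of the primary endpoint (4.8), the horizon of the primary analysis (5.3) and the start of the ITT tail (7.1). Week 45 is not a scheduled visit, and it overlaps the ITT tail by 45 − 41 = 4 weeks.

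**One to four injections.** The Week 41 passages do not separate 8 from 12 weeks here, because both ends fall before Week 41. Support for 8 weeks is 9.5.5 itself and, by analogy only, the per-protocol tail rule in 7.1.

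**Early stoppers, secondary.** The assumption is that the safety tables use the ITT tail start. The interval from a participant's own injection-phase end to Week 41 is then:

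- Cohort 1: 41 − 17 = 24 weeks after one injection, 41 − 29 = 12 after two.
- Cohort 2 with the 9.5.5 rule: 41 − 13 = 28, 41 − 17 = 24, 41 − 25 = 16 and 41 − 33 = 8 weeks after one to four.

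This interval is in neither the injection nor the tail column of Tables 9–12 and 19. The Appendix algorithm assigns every AE after the first injection date to the injection phase and states no end.

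**The case against.** The best defence is that 9.5.5 is the most specific text, gives an explicit rule per cohort, and would probably be followed. For a full course only a participant free of any qualifying event for 36 weeks, with a first event in the next 4, changes status, and no visit is scheduled in those 4 weeks. This stands, and it limits the severity. It does not remove the contradiction in the definition of a primary endpoint.

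Several stronger readings are tempting but not supported:

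- *The Week 41 text proves 8 weeks for everyone in Cohort 2.* It does so for full courses only.
- *The 9.5.5 rule gives the cohorts equal windows, so the aggregate analysis needs it.* It gives 36 weeks in both after a full course. After one injection it gives 12 weeks in Cohort 1 and 8 in Cohort 2, whereas 3.1 gives 12 in both. Which rule equalises depends on the injections received.
- *Section 7.1 assigns Cohort 2 participants windows of 20 or 24 weeks after their last injection.* Calling three injections the complete course shows that the sentence describes Cohort 1. The defect is that no Cohort 2 set is given.
- *The SMC labels for Weeks 5–41 confirm the window.* Section 10.2.1 also attaches Weeks 5–105/109 to the injection phase, so its labels are weak evidence.
- *The treatment comparison is biased.* Either rule applies to both arms. Placebo follow-up stops after unblinding (4.3), but the SAP does not give the timing needed to show unequal observation in Weeks 41–45.
- *Events of early stoppers are lost.* The on-treatment columns include them. The Appendix algorithm is introduced as separating oral from injection phase, so its missing end is a gap and not a contradiction of 7.1.

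**Conclusion.** The contradiction is real and in current text. For Cohort 2 the primary safety window ends 12 weeks after the last injection in 3.1 and 7.1 and 8 weeks after it in 9.5.5, and 7.1 gives no Cohort 2 end weeks. For a full course the SAP's other statements fit 8 weeks only. For shorter courses the support is narrower.

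The difference is always 4 weeks: 11% of the 36-week window after a full course, rising to 50% after a single injection. The SAP gives no event rate and no number of early stoppers, so the effect on the proportion cannot be derived; it is likely small. These figures assume injections in their scheduled weeks. This is a should-fix reconciliation of the primary endpoint definition, not evidence that a result would be biased. The early-stopper interval is a secondary matter of table columns.

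**What to change.** 1. Check the endpoint in the protocol version that SAP Section 1 cites (version 3.0). Then state one cohort-specific window in the same words in 3.1, 7.1 and 9.5.5.
2. In 7.1 print a Cohort 2 set for one to five injections. If the 9.5.5 rule is confirmed, it is Weeks 13, 17, 25, 33 and 41. If 12 weeks is confirmed, it is Weeks 17, 21, 29, 37 and 45; 9.5.5, the tail start and the Week 41 text must then be reconciled with it. Label the existing set as Cohort 1.
3. State that Table 19(b) and the person-time in 9.5.5 use this window.
4. Secondary: say which column of Tables 9–12 and 19 holds events between an early stopper's injection-phase end and Week 41, and give the Appendix injection-phase rule a matching end.

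The cost is SAP wording and minor programming. No new data are needed.

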3.2 Secondary Objectives and Endpoints

Secondary Objectives

- Evaluate the safety and tolerability of GSK1265744 (daily oral 744 + 744LA) for 76 weeks of follow-up after final injection (each cohort will be analyzed separately)
- Evaluate the safety and tolerability of oral 744 from Week 0 to Week 5

- Evaluate the pharmacokinetics of 744LA administered as 800 mg IM every 12 weeks for 52 weeks of follow-up after final injection
- Evaluate differential pharmacokinetics of 744LA in participants by age, gender, race, ethnicity, weight, body mass index (BMI), and smoking status
- Evaluate the acceptability of 744LA injections
- Evaluate the effect of 744LA on sexual risk behavior by change from enrollment for repeat assessments to during the study period
- Evaluate HIV incidence and antiretroviral drug resistance, if any participants acquire HIV infection during the study
- Evaluate the safety, tolerability and pharmacokinetics of 744LA in the subset of women who use a hormone-based contraceptive

Secondary Endpoints

- Proportion of participants who discontinue either oral or injectable study product for reasons of toxicity, tolerability, or acceptability prior to completion of the full oral and injectable phases
- Proportion of participants experiencing Grade 2 or higher clinical AEs and laboratory abnormalities during 52 weeks following final injection (safety) and any AE that leads to discontinuation (tolerability) during the aggregate oral and injectable phases
- Proportion of participants experiencing Grade 2 or higher clinical AEs and laboratory abnormalities (safety) and any AE that leads to discontinuation (tolerability) in the oral phase and washout period
- Plasma drug levels of GSK1265744 at designated time points after each injection of 744LA (by cohort only)
- Plasma drug levels of GSK1265744 at designated time points after each injection of 744LA stratified by age, gender, race, ethnicity, weight, BMI, and smoking status
- Proportion of participants willing to use an injectable agent such as the study product for HIV prevention in the future
- Change from enrolment of self-reported sexual behaviour (number of sexual partners, episodes of unprotected anal and/or vaginal intercourse) during the study period using a standardized assessment tool (in aggregate only)
- Number of incident HIV infections through the study period, including number with treatment emergent resistance

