9.6 Tolerability

To assess tolerability of 744 LA, the proportion (with 95% CI) of subjects who terminate from receiving injections prior to the full course due to AEs, intolerance of injection, frequency of injections, or burden of procedures related to injections out of those subjects that received at least one injection by cohort and treatment arm will be provided. The proportion will be compared between the treatment arms by cohort and in aggregate using Fisher Exact test.

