9.7.1 Association between Pharmacokinetics and Baseline Characteristics

To evaluate differential pharmacokinetics of 744LA in participants by age, gender, race, ethnicity, weight, body mass index (BMI), and smoking status, we will use GEE regression model to account the correlations of the PK parameters following three injections in Cohort 1 or five injections in Cohort 2. The analysis will be performed separately for each cohort. The associations between the PK parameters and the predictors will be tested in univariate models (include one predictor in each model) and

in a multivariate model (include all predictors). Each model will be adjusted for sites (US vs. Non-US sites) by cohort.

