11.2 Safety and Tolerability Analysis

11.2.1 Lists of Tables

Table 8 Permanent discontinuation of study regimen by treatment arm (a) during the oral phase, (b) during the injection phase, and (c) during the on-treatment

Table 9 Adverse experiences by MedDRA preferred term and severity (ordered by system organ class) (a) during the oral phase, (b) during the injection phase, (c) during the tail phase, and (d) during the on-treatment

Table 10 Adverse experiences by MedDRA preferred term and severity – including severe, potential life-threatening or fatal events only (a) during the oral phase, (b) during the injection phase, (c) during the tail phase, and (d) during the on-treatment

Table 11 Adverse experiences by MedDRA preferred term and relationship to study product (a) during the oral phase, (b) during the injection phase, (c) during the tail phase, and (d) during the on-treatment

Table 12 Elevation of liver chemistry and other lab test events (a) during the oral phase, (b) during the injection phase, (c) during the tail phase, and (d) during the on-treatment

Table 13 Summary of Injection Site Reaction Characteristics

Table 14 Summary of characteristics of common ISR symptoms

Table 15 Summary of change in laboratory test at follow up from baseline by visit and cohort

Table 16 Summary of ECG values by treatment arm and visit

Table 17 Summary of maximum change in corrected QTc intervals by category for change from baseline

Table 18 Listing of expedited adverse events (EAE) or serious adverse events (SAE) with the details of the events including severity, relationship to study product, time between onset and last injection, number of injections received (if the events occurring after the 1st injection), and a summary of the event

Table 19 Proportion of participants experiencing any Grade 2 or higher clinical AEs and laboratory abnormalities that occur (a) during the oral phase, (b) during the injection phase (c) during the tail phase, and (d) during the on-treatment period

Table 20 The proportion of participants who discontinue the study product for reasons of toxicity, tolerability, or acceptability (a) prior to completion of the full oral phase and (b) prior to completion of the full injection phase.

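### The primary tolerability endpoint sets the full course at 3 injections, but Cohort 2 is scheduled for 5

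*SAP*

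**What the plan says.** Section 3.1 lists a primary objective for each regimen, then a single tolerability endpoint covering participants "who discontinue receiving injections prior to the full course of 3 injections due to intolerance of injection (including but not limited to ISR", the frequency of injections, procedure burden or any AE. No cohort is named, and the next sentence allows the cohorts to be aggregated.

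Section 2.4 schedules Cohort 2 injections "at five time points at 4 and 8 week intervals as: Week 5, Week 9, Week 17, Week 25, and Week 33". Sections 2.3 and 4.4 list the same five weeks, and 9.7.1 refers to PK parameters "following three injections in Cohort 1 or five injections in Cohort 2".

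Section 7.1 uses both counts. Its Tail Phase text describes the full set as "3 injections for cohort 1 and 5 injections for cohort 2". Its Injection Phase text reads "For the participants who complete all three injections, the injection phase assessment window is the time between Week 5 and Week 41 visits", with no cohort qualifier.

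Section 9.6 estimates the proportion "who terminate from receiving injections prior to the full course due to AEs, intolerance of injection, frequency of injections, or burden of procedures", by cohort and arm, and compares arms by Fisher's exact test by cohort and in aggregate. It gives no number of injections and no cross-reference.

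**The concern.** The only number attached to this primary endpoint fits Cohort 1 alone. In Cohort 2, a participant who has had three injections has completed the course as 3.1 defines it, although two more are scheduled. A programmer who codes 3.1 literally will not count a stop after injection 3 or 4, whatever its reason. One who reads 9.6 with the schedule will count it.

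Three things are at stake. The Cohort 2 proportion under 3.1 can only be equal to or lower than the five-injection proportion, so any bias is toward good tolerability. The aggregate would combine stopping windows of different length. And if the choice is left until the data are unblinded, it becomes a post hoc decision about a primary endpoint.

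**Working it through.** **Step 1. Check the stated number against the schedule (2.3, 2.4).**

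- Cohort 1: Weeks 5, 17, 29 = 3 injections. This matches the 3 in section 3.1.
- Cohort 2: Weeks 5, 9, 17, 25, 33 = 5 injections. This does not match.

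**Step 2. Count the stopping points.** A participant can stop early after any injection except the last, so Cohort 2 has 4 stopping points (after injections 1 to 4). Under 3.1 only stops after injections 1 and 2 count, so 2 of 4 are left out.

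**Step 3. Compare the windows from first injection to the injection that completes the course.**

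- Cohort 1: 29 − 5 = 24 weeks.
- Cohort 2 under 3.1: 17 − 5 = 12 weeks.
- Cohort 2 over five injections: 33 − 5 = 28 weeks.
- Omitted in Cohort 2: 33 − 17 = 16 weeks, and 16/28 = 57%.

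**Step 4. Illustrate the size.** The SAP gives no expected stopping rate, so every risk below is an assumption. Let r1 to r4 be the risks of a qualifying stop after injections 1 to 4.

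- Counted under 3.1: 1 − (1 − r1)(1 − r2)
- Five-injection course: 1 − (1 − r1)(1 − r2)(1 − r3)(1 − r4)
- Share missed: 1 − (first ÷ second)

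For a constant weekly risk w, the intervals are 4, 8, 8 and 8 weeks. The two quantities become 1 − (1 − w)^12 and 1 − (1 − w)^28.

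| Assumed risk of stopping | Counted under 3.1 | Five-injection course | Share missed |
|---|---|---|---|
| 1% after each injection | 2.0% | 3.9% | 49.5% |
| 2% after each injection | 4.0% | 7.8% | 49.0% |
| 5% after each injection | 9.8% | 18.5% | 47.4% |
| 0.1% per week | 1.2% | 2.8% | 56.8% |
| 0.25% per week | 3.0% | 6.8% | 56.3% |
| 0.5% per week | 5.8% | 13.1% | 55.4% |
| Falling: 4, 2, 1, 0.5% | 5.9% | 7.3% | 19.2% |
| Rising: 0.5, 1, 2, 4% | 1.5% | 7.3% | 79.6% |

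Worked example at 2%: 1 − 0.98² = 0.0396; 1 − 0.98⁴ = 0.0776; 1 − 0.0396/0.0776 = 49.0%.

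**Step 5. Convert to events.** Section 2.4 gives about 66 active participants in Cohort 2. This is an upper bound on the denominator, because it assumes all of them reach injection 1.

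- Falling pattern: 66 × 0.0592 = 3.9 against 66 × 0.0733 = 4.8, so about 1 event missed.
- Rising pattern: 66 × 0.0150 = 1.0 against 4.8, so about 4 events missed.

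**Step 6. Compare cohorts at the same risk.** With 0.25% per week in both, Cohort 1 over 24 weeks gives 1 − 0.9975^24 = 5.8%. Cohort 2 gives 3.0% under 3.1 and 6.8% over its five-injection course. The shortfall of 3.0% against 5.8% comes from the definition alone.

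**The case against.** The strongest reply is that nobody would read 3.1 this way. The second primary objective in 3.1 itself describes two plus three Cohort 2 injections and runs to Week 41, so ending Cohort 2 tolerability at Week 17 conflicts with the section's own aim. Section 9.6 is the operative analysis text; it drops the number and reports by cohort. The one cohort-specific statement of a full set, in 7.1, gives 3 and 5. The Injection Phase wording in 7.1 goes on to map two injections to Week 29 and one to Week 17, which is plainly the Cohort 1 schedule and looks like text that was not extended to Cohort 2. On this view the intent is clear.

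That is a fair reading of intent, and probably the right one. It does not settle the definition. Section 9.6 cites neither 3.1 nor 7.1, the 3-and-5 statement in 7.1 serves only the per-protocol tail window, and 3.1 is the only place that attaches a number to this endpoint.

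Two further points stand and limit the finding. First, late stops are not lost. They fall under the secondary endpoint in 3.2 ("Proportion of participants who discontinue either oral or injectable study product for reasons of toxicity, tolerability, or acceptability"), the tabulation of reasons in 9.5.6, Tables 8 and 20, and the discontinuation Kaplan-Meier figures. However, Table 20 ("The proportion of participants who discontinue the study product for reasons of toxicity, tolerability, or acceptability") uses a different list of reasons and does not replace the primary proportion. Second, the size is unknown, and the protocol, which may be the source of the wording, is not at hand.

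**Conclusion.** The concern holds. As written, the full course in the primary tolerability endpoint is wrong for Cohort 2, and the rest of the SAP does not resolve it. If 3.1 governs, stops after injections 3 and 4 cannot be primary events. The Cohort 2 proportion then omits half its stopping points and 57% of the time between first and last injection.

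The direction is certain: the proportion cannot rise and will usually fall. The size is not. It is 47% to 50% of events with equal risk of 1% to 5% per injection, 55% to 57% with equal weekly risk of 0.1% to 0.5%, 19% if risk falls and 80% if it rises over the course. All of these rest on assumed risks. The effect is limited to the primary tolerability proportion, by cohort and in aggregate, and its Fisher tests. Because a primary endpoint has two possible numerators, this must be fixed before the results are unblinded.

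**What to change.** Before the unblinded Week 41 analysis:

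- In 3.1 and 9.6, state that the full course is 3 injections in Cohort 1 and 5 in Cohort 2, as the SAP's own schedule in 2.3 and 2.4 lists.
- Reconcile the unqualified three-injection wording of the Injection Phase in 7.1 with this.
- Minor: use one list of reasons. Section 3.1 counts burden from study procedures in general, while 9.6 counts only procedures tied to injections. Since 3.1 is the endpoint definition, 9.6 should repeat it unless the protocol says otherwise.
- Keep Table 20 for the secondary endpoint, and give the primary tolerability proportion its own entry by cohort and arm.
- If the protocol carries the same three-injection wording, clarify it there as well.

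The cost is a few words in three sections, one separately reported proportion, and possibly a protocol clarification. The Cohort 2 figure may look less favourable. The stopping windows become 24 and 28 weeks, which are closer but still not identical, and the aggregate should say so.
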